8.2.8 Clinic Visit, All Treatment Arms

**Visit 07, Day 23 (Window: Day 2+1 day post second study vaccination),
Treatment Arms 1 and 4**

**Visit 09, Day 122 (Window: Day 2+1 day post second study vaccination),
Treatment Arms 2, 3, 5, and 6**

- Interim medical history, including an assessment for new medical conditions, stability of chronic diseases and symptoms suggestive of PIMMCs, will be obtained by interview of subjects and any changes since the previous clinic visit or phone call will be noted.
- All concomitant medications (including solicitation for receipt of any non-study influenza vaccines) will be recorded on the appropriate DCF.
- All AE/SAEs will be recorded on the appropriate DCF. Note: AEs will be limited to SAEs and MAAEs, including NOCMCs and PIMMCs, for subjects who are discontinued from receipt of the second study vaccination and being followed for safety.
- Memory Aid information will be reviewed with subjects.
- A targeted physical examination, including an assessment for signs suggestive of PIMMCs, may be performed, if indicated based on review of interim medical history, by a study clinician licensed to make medical diagnoses and listed on the Form FDA 1572 as the site PI or sub-investigator.

- The second study vaccination site will be examined.
- Approximately 4 mL of venous blood will be collected for cellular immunology assays.
- Approximately 16 mL of venous blood will be collected for future research.

8.2.9 Clinic Visit, All Treatment Arms

Visit 08, Day 25 (Window: Day 4+1 day post second study vaccination), Treatment Arms 1 and 4

Visit 10, Day 124 (Window: Day 4+1 day post second study vaccination), Treatment Arms 2, 3, 5, and 6

- Interim medical history, including an assessment for new medical conditions, stability of chronic diseases and symptoms suggestive of PIMMCs, will be obtained by interview of subjects and any changes since the previous clinic visit or phone call will be noted.
- All concomitant medications (including solicitation for receipt of any non-study influenza vaccines) will be recorded on the appropriate DCF.
- All AE/SAEs will be recorded on the appropriate DCF. Note: AEs will be limited to SAEs and MAAEs, including NOCMCs and PIMMCs, for subjects who are discontinued from receipt of the second study vaccination and being followed for safety.
- Memory Aid information will be reviewed with subjects.
- A targeted physical examination, including an assessment for signs suggestive of PIMMCs, may be performed, if indicated based on review of interim medical history, by a study clinician licensed to make medical diagnoses and listed on the Form FDA 1572 as the site PI or sub-investigator.
- The second study vaccination site will be examined.
- Approximately 8 mL of venous blood will be collected for cellular immunology assays.
- Approximately 16 mL of venous blood will be collected for future research.

8.2.10 Clinic Visit, All Treatment Arms

Visit 09, Day 29 (Window: Day 8-1/+2 days post second study vaccination), Treatment Arms 1 and 4

Visit 11, Day 128 (Window: Day 8-1/+2 days post second study vaccination), Treatment Arms 2, 3, 5, and 6

- Interim medical history, including an assessment for new medical conditions, stability of chronic diseases and symptoms suggestive of PIMMCs, will be obtained by interview of subjects and any changes since the previous clinic visit or phone call will be noted.
- All concomitant medications (including solicitation for receipt of any non-study influenza vaccines) will be recorded on the appropriate DCF.
- All AE/SAEs will be recorded on the appropriate DCF. Note: AEs will be limited to SAEs and MAAEs, including NOCMCs and PIMMCs, for subjects who are discontinued from receipt of the second study vaccination and being followed for safety.
- Memory Aid information will be reviewed with subjects.
- A targeted physical examination, including an assessment for signs suggestive of PIMMCs, may be performed, if indicated based on review of interim medical history, by a study clinician licensed to make medical diagnoses and listed on the Form FDA 1572 as the site PI or sub-investigator.
- The second study vaccination site will be examined.
- Approximately 10 mL of venous blood will be collected for clinical safety labs (WBC, Hgb, PLT, ALT, T. Bili, Cr) to be performed by the central (clinical) laboratory.
- Approximately 44 mL of venous blood will be collected for cellular immunology assays.
- Approximately 21 mL of venous blood will be collected for future research.

Note: Subjects that complete this visit on Day 7 will be reminded to complete their Memory Aid through the end of Day 8, and study personnel will contact these subjects by phone to review their Memory Aid information and solicit any AE/SAEs and concomitant medications (including solicitation for receipt of any non-study influenza vaccines). Based on the information collected, subjects may be asked to return to the clinic for evaluation.

8.2.11 Clinic Visit, All Treatment Arms

Visit 10, Day 36 (Window: 15±1 day post second study vaccination), Treatment Arms 1 and 4

Visit 12, Day 135 (Window: Day 15±1 day post second study vaccination), Treatment Arms 2, 3, 5, and 6

- Interim medical history, including an assessment for new medical conditions, stability of chronic diseases and symptoms suggestive of PIMMCs, will be obtained by interview of subjects and any changes since the previous clinic visit or phone call will be noted.
- All concomitant medications (including solicitation for receipt of any non-study influenza vaccines) will be recorded on the appropriate DCF.
- All AE/SAEs will be recorded on the appropriate DCF. Note: AEs will be limited to SAEs and MAAEs, including NOCMCs and PIMMCs, for subjects who are discontinued from receipt of the second study vaccination and being followed for safety.
- A targeted physical examination, including an assessment for signs suggestive of PIMMCs, may be performed, if indicated based on review of interim medical history, by a study clinician licensed to make medical diagnoses and listed on the Form FDA 1572 as the site PI or sub-investigator.
- Approximately 8 mL of venous blood will be collected for cellular immunology assays.
- Approximately 16 mL of venous blood will be collected for future research.

8.2.12 Clinic Visit, All Treatment Arms

Visit 11, Day 43 (Window: Day 22+7 days post second study vaccination), Treatment Arms 1 and 4

Visit 13, Day 142 (Window: Day 22+7 days post second study vaccination), Treatment Arms 2, 3, 5, and 6

- Interim medical history, including an assessment for new medical conditions, stability of chronic diseases and symptoms suggestive of PIMMCs, will be obtained by interview of subjects and any changes since the previous clinic visit or phone call will be noted.
- All concomitant medications (including solicitation for receipt of any non-study influenza vaccines) will be recorded on the appropriate DCF.

- All AE/SAEs will be recorded on the appropriate DCF. Note: AEs will be limited to SAEs and MAAEs, including NOCMCs and PIMMCs, for subjects who are discontinued from receipt of the second study vaccination and being followed for safety.
- A targeted physical examination, including an assessment for signs suggestive of PIMMCs, may be performed, if indicated based on review of interim medical history, by a study clinician licensed to make medical diagnoses and listed on the Form FDA 1572 as the site PI or sub-investigator.
- Approximately 15 mL of venous blood will be collected for serological assays.
- Approximately 16 mL of venous blood will be collected for future research.

8.2.13 Safety Follow-up, Phone Call, All Treatment Arms

**Visit 12, Day 82 (Window: Day 61±7 days post second study vaccination),
Treatment Arms 1 and 4**

**Visit 14, Day 181 (Window: Day 61±7 days post second study vaccination),
Treatment Arms 2, 3, 5, and 6**

Subjects will be contacted by phone to query for safety events and receipt of any non-study influenza vaccines. AEs limited to SAEs and MAAEs, including NOCMCs and PIMMCs, that have occurred since the previous clinic visit or phone call will be solicited. Based on the information collected, subjects may be asked to return to the clinic for evaluation.

8.2.14 Clinic Visit, All Treatment Arms

**Visit 13, Day 112 (Window: Day 91±14 days post second study vaccination),
Treatment Arms 1 and 4**

**Visit 15, Day 211 (Window: Day 91±14 days post second study vaccination),
Treatment Arms 2, 3, 5, and 6**

- Interim medical history, including an assessment for new medical conditions, stability of chronic diseases and symptoms suggestive of PIMMCs, will be obtained by interview of subjects and any changes since the previous clinic visit or phone call will be noted.
- Receipt of any non-study influenza vaccines will be recorded on the appropriate DCF.
- AEs limited to SAEs and MAAEs, including NOCMCs and PIMMCs, that have occurred since the previous clinic visit or phone call will be solicited.

- A targeted physical examination, including an assessment for signs suggestive of PIMMCs, may be performed, if indicated based on review of interim medical history, by a study clinician licensed to make medical diagnoses and listed on the Form FDA 1572 as the site PI or sub-investigator.
- Approximately 40 mL of venous blood will be collected for cellular immunology assays.
- Approximately 16 mL of venous blood will be collected for future research.

8.2.15 Safety Follow-up, Phone Call, All Treatment Arms

**Visit 14, Day 142 (Window: Day 121±14 days post second study vaccination),
Treatment Arms 1 and 4**

**Visit 16, Day 241 (Window: Day 121±14 days post second study vaccination),
Treatment Arms 2, 3, 5, and 6**

Subjects will be contacted by phone to query for safety events and receipt of any non-study influenza vaccines. AEs limited to SAEs and MAAEs, including NOCMCs and PIMMCs, that have occurred since the previous clinic visit or phone call will be solicited. Based on the information collected, subjects may be asked to return to the clinic for evaluation.

8.2.16 Clinic Visit, All Treatment Arms

**Visit 15, Day 202 (Window: Day 181±14 days post second study vaccination),
Treatment Arms 1 and 4**

**Visit 17, Day 301 (Window: Day 181±14 days post second study vaccination),
Treatment Arms 2, 3, 5, and 6**

- Interim medical history, including an assessment for new medical conditions, stability of chronic diseases and symptoms suggestive of PIMMCs, will be obtained by interview of subjects and any changes since the previous clinic visit or phone call will be noted.
- Receipt of any non-study influenza vaccines will be recorded on the appropriate DCF.
- AEs limited to SAEs and MAAEs, including NOCMCs and PIMMCs, that have occurred since the previous clinic visit or phone call will be solicited.
- A targeted physical examination, including an assessment for signs suggestive of PIMMCs, may be performed, if indicated based on review of interim medical history, by a study clinician licensed to make medical diagnoses and listed on the Form FDA 1572 as the site PI or sub-investigator.

- Approximately 15 mL of venous blood will be collected for serological assays.
- Approximately 32 mL of venous blood will be collected for cellular immunology assays.
- Approximately 16 mL of venous blood will be collected for future research.

8.3 Final Visit

8.3.1 Safety Follow-up, Phone Call, All Treatment Arms

**Visit 16, Day 387 (Window: Day 366±14 days post second study vaccination),
Treatment Arms 1 and 4**

**Visit 18, Day 486 (Window: Day 366±14 days post second study vaccination),
Treatment Arms 2, 3, 5, and 6**

Subjects will be contacted by phone to query for safety events. AEs limited to SAEs and MAAEs, including NOCMCs and PIMMCs, that have occurred since the previous clinic visit or phone call will be solicited. Based on the information collected, subjects may be asked to return to the clinic for evaluation.

8.4 Early Termination Visit (if needed)

The following activities will be performed at the Early Termination Visit on subjects who withdraw, or are withdrawn or terminated from this trial:

- Interim medical history, including an assessment for new medical conditions, stability of chronic diseases and symptoms suggestive of PIMMCs, will be obtained by interview of subjects and any changes since the previous clinic visit or phone call will be noted.
- All concomitant medications will be recorded on the appropriate DCF (if prior to 21 days after the last study vaccination). Receipt of any non-study influenza vaccines will also be recorded on the appropriate DCF (if within 180 days after the last study vaccination).
- All AE/SAEs will be recorded on the appropriate DCF. AEs limited to SAEs and MAAEs, including NOCMCs and PIMMCs, that have occurred since the previous clinic visit or phone call will be solicited (if after 21 days after the last study vaccination).
- Memory Aid information will be reviewed with subjects (if within 7 days after the last study vaccination).

- Vital signs, including oral temperature, pulse and BP, may be obtained if indicated. Subjects must not eat or drink anything hot or cold, or smoke within 10 minutes prior to taking oral temperature.
- A targeted physical examination, including an assessment for signs suggestive of PIMMCs, may be performed, if indicated based on review of interim medical history, by a study clinician licensed to make medical diagnoses and listed on the Form FDA 1572 as the site PI or sub-investigator.
- The study vaccination site will be examined (if within 7 days after the last study vaccination).
- Post-administration reactogenicity assessments will be performed (if within 7 days after the last study vaccination).
- Approximately 10 mL of venous blood will be collected for clinical safety labs (WBC, Hgb, PLT, ALT, T. Bili, Cr) to be performed by the central (clinical) laboratory (if within 7 days after the last study vaccination).
- Approximately 15 mL of venous blood will be collected for serological assays (if within 21 days after the last study vaccination).
- Approximately 24 mL of venous blood will be collected for cellular immunology assays (if within 21 days after the last study vaccination).
- Approximately 16 mL of venous blood will be collected for future research (if within 21 days after the last study vaccination).

8.5 Unscheduled Visit (if needed)

An Unscheduled Visit may occur at any time during this trial. Any of the following activities may be performed:

- Interim medical history, including an assessment for new medical conditions, stability of chronic diseases and symptoms suggestive of PIMMCs, will be obtained by interview of subjects and any changes since the previous clinic visit or phone call will be noted (if indicated).
- All concomitant medications will be recorded on the appropriate DCF (if prior to 21 days after the last study vaccination). Receipt of any non-study influenza vaccines will also be recorded on the appropriate DCF (if within 180 days after the last study vaccination).

- All AE/SAEs will be recorded on the appropriate DCF. AEs limited to SAEs and MAAEs, including NOCMCs and PIMMCs, that have occurred since the previous clinic visit or phone call will be solicited (if after 21 days after the last study vaccination).
- Memory Aid information will be reviewed with subjects (if within 7 days after the last study vaccination).
- Vital signs, including oral temperature, pulse and BP, may be obtained if indicated. Subjects must not eat or drink anything hot or cold, or smoke within 10 minutes prior to taking oral temperature.
- A targeted physical examination, including an assessment for signs suggestive of PIMMCs, may be performed, if indicated based on review of interim medical history, by a study clinician licensed to make medical diagnoses and listed on the Form FDA 1572 as the site PI or sub-investigator.
- The study vaccination site will be examined (if within 7 days after the last study vaccination).
- Post-administration reactogenicity assessments will be performed (if within 7 days after the last study vaccination).
- Approximately 10 mL of venous blood will be collected for clinical safety labs (WBC, Hgb, PLT, ALT, T. Bili, Cr) to be performed by the central (clinical) laboratory (if indicated).
- Approximately 15 mL of venous blood will be collected for serological assays (if within 21 days after the last study vaccination).
- Approximately 24 mL of venous blood will be collected for cellular immunology assays (if within 21 days after the last study vaccination).
- Approximately 16 mL of venous blood will be collected for future research (if within 21 days after the last study vaccination).

9 ASSESSMENT OF SAFETY

9.1 Specification of Safety Parameters

Safety will be assessed by the frequency and severity of:

1. SAEs occurring from the time of the first study vaccination through approximately 12 months after the last study vaccination.
2. Solicited AEs – reactogenicity events occurring from the time of each study vaccination through 7 days after each study vaccination:
 - a) Injection site reactions including pruritus, ecchymosis, erythema, induration (hardness)/edema (swelling), pain, and tenderness.
 - b) Systemic reactions including fever, feverishness, fatigue, malaise, myalgia, arthralgia, headache, and nausea.
3. Clinical safety laboratory AEs occurring from the time of each study vaccination through approximately 7 days after each study vaccination. Parameters to be evaluated include WBC, Hgb, PLT, ALT, T. Bili, Cr.
4. Unsolicited AEs –non-serious AEs occurring from the time of each study vaccination through approximately 21 days after each study vaccination.
5. MAAEs, including NOCMCs and PIMMCs, occurring from the time of the first study vaccination through approximately 12 months after the last study vaccination.

9.2 Methods and Timing for Assessing, Recording and Analyzing Safety Parameters

9.2.1 Adverse Events

Adverse Event (AE): ICH E6 GCP defines an AE as any untoward medical occurrence in a patient or clinical investigation subject administered a pharmaceutical product regardless of its causal relationship to the study treatment. The FDA defines an AE as any untoward medical occurrence associated with the use of a drug in humans, whether or not considered drug related.

An AE can therefore be any unfavorable and unintended sign (including an abnormal laboratory finding), symptom or disease temporally associated with the use of a medicinal (investigational)

product. The occurrence of an AE may come to the attention of study personnel during study visits and interviews of a study recipient presenting for medical care, or upon review by a study monitor.

AEs, including solicited injection site and systemic (subjective and quantitative) reactions, not meeting the protocol-defined criteria for SAEs, will be recorded on the appropriate DCF and entered into the eCRF. Information to be collected for unsolicited non-serious AEs includes event description, date of onset, licensed study physician's assessment of severity and relationship to study product or alternate etiology (if not related to study product) (assessed only by those with the training and authority to make a diagnosis and listed on the Form FDA 1572 as the site PI or sub-investigator), date of resolution, seriousness, and outcome. AEs occurring during the trial-collection and reporting period will be documented appropriately regardless of relationship to study product. AEs will be followed through resolution.

Any medical condition that is present at the time that the subject is screened will be considered as baseline and not reported as an AE. However, if the severity of any pre-existing medical condition increases, it will be recorded as an AE.

AEs must be assessed for severity and relationship to study product (see definitions below). AEs characterized as intermittent require documentation of onset and duration of each episode. The start and stop date of each reported AE will be recorded on the appropriate DCF and entered into the eCRF.

Medically-Attended Adverse Events (MAAEs): For each unsolicited AE experienced, the subject will be asked if he/she had received medical attention, defined as hospitalization, an emergency room visit or an otherwise unscheduled visit to or from medical personnel for any reason. AEs characterized by such unscheduled medical care will be designated as MAAEs.

New-Onset Chronic Medical Conditions (NOCMCs): NOCMCs are defined as any new ICD-10 diagnosis (10th revision of the International Statistical Classification of Diseases and Related Health Problems) that is applied to the subject during the course of the study, after receipt of the study agent, that is expected to continue for at least 3 months and requires continued health care intervention.

Potentially Immune-Mediated Medical Conditions (PIMMCs): PIMMCs constitute a group of AEs that includes diseases which are clearly autoimmune in etiology and other inflammatory and/or neurologic disorders which may or may not have autoimmune etiologies. PIMMCs currently in effect are presented in [Appendix C: List of Potentially Immune-Mediated Medical Conditions](#).

Severity of Event: AEs will be assessed by a licensed study physician listed on the Form FDA 1572 as the site PI or sub-investigator using a protocol-defined grading system (see [Sections 9.2.2](#) and [9.2.3](#)). For events not included in the protocol-defined grading system, the following guidelines will be used to quantify severity:

- Mild (Grade 1): Events require minimal or no treatment and do not interfere with the subject's daily activities.
- Moderate (Grade 2): Events result in a low level of inconvenience or concern with therapeutic measures. Moderate events may cause some interference with functioning and daily activities.
- Severe (Grade 3): Events interrupt the subject's daily activities and may require systemic drug therapy or other treatment. Severe events are usually incapacitating.

Relationship to Study Product: The licensed study physician's assessment of an AE's relationship to study product is part of the documentation process, but it is not a factor in determining what is or is not reported in this trial. If there is any doubt as to whether a clinical observation is an AE, the event should be reported. The relationship to study product must be assessed for AEs using the terms: related or not related. In a clinical trial, the study product must always be suspect. To help assess, the following guidelines are used:

- Related – There is a reasonable possibility that the study product caused the AE. Reasonable possibility means that there is evidence to suggest a causal relationship between the study product and the AE.
- Not Related – There is not a reasonable possibility that the administration of the study product caused the event.

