3.2.2 Secondary

Safety:

- Occurrence of all unsolicited non-serious AEs from the time of each study vaccination through approximately 21 days after each study vaccination.
- Occurrence of all MAAEs, including NOCMCs and PIMMCs, from the time of the first study vaccination through approximately 12 months after the last study vaccination.

Immunogenicity:

- For HAI and Neut antibodies, percentage of subjects achieving seroconversion against the influenza A/H7N9 study vaccine viruses approximately 21 days after the first study vaccination as well as immediately prior to and approximately 180 days after the second study vaccination.
- For HAI and Neut antibodies, percentage of subjects achieving titer \geq 1:40 against the influenza A/H7N9 study vaccine viruses immediately prior to each study vaccination, approximately 21 days after the first study vaccination and approximately 180 days after the second study vaccination.

- GMTs of serum HAI and Neut antibodies against the influenza A/H7N9 study vaccine viruses immediately prior to each study vaccination, approximately 21 days after the first study vaccination and approximately 180 days after the second study vaccination.

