16.2.7 Adverse Events

Listing 11: 16.2.7.1 - Solicited Events – Systemic Symptoms

| Subject ID | Study Group | Vaccination Number | Post Dose Day | Assessment ¹ | Symptom | Severity | Attributed to Alternate Etiology? ² | Alternate Etiology |
|------------|-------------|--------------------|---------------|-------------------------|---------|----------|--|--------------------|
| | | | | MA | | | | |
| | | | | Clinic | | | | |
| | | | | | | | | |
| | | | | | | | | |

¹ MA = Data reported by subject on the Memory Aid and reviewed by clinic staff and reported in Solicited Events eCRF.
Clinic = Data collected by clinic staff during physical exam or symptom assessment (treatment administration record, in-clinic assessment, etc.).
² Grade 3 events only.

Listing 12: 16.2.7.2 - Solicited Events – Local Symptoms

| Subject ID | Study Group | Vaccination Number | Product Received ¹ | Post Vaccination Day | Assessment ¹ | Symptom | Severity |
|------------|-------------|--------------------|-------------------------------|----------------------|-------------------------|---------|----------|
| | | | | | MA | | |
| | | | | | Clinic | | |
| | | | | | | | |
| | | | | | | | |

¹ MA = Data reported by subject on the Memory Aid and reviewed by clinic staff and reported in Solicited Events eCRF.
Clinic = Data collected by clinic staff during physical exam or symptom assessment (treatment administration record, in-clinic assessment, etc.).

Listing 13: 16.2.7.3 - Unsolicited Adverse Events

| Adverse Event | Associated with Vac # | # of Days Post Associated Vac (Duration) | Severity | SAE? MAAE? PIMMC? | Relationship to Study Vaccination | In Not Related, Alternative Etiology | Action Taken with Study Vaccination | Subject Discontinued Due to AE | Outcome | MedDRA® System Organ Class | MedDRA® Preferred Term |
|---|-----------------------|--|----------|-----------------------------------|-----------------------------------|--------------------------------------|-------------------------------------|--------------------------------|---------|----------------------------|------------------------|
| Subject ID: , Study Group: , AE Number: | | | | | | | | | | | |
| | | | | SAE: No MAAE: Yes PIMMC: No | | | | | | | |
| Comments: | | | | | | | | | | | |
| Subject ID: , Study Group: , AE Number: | | | | | | | | | | | |
| | | | | | | | | | | | |
| Comments: | | | | | | | | | | | |
| Note: For additional details about SAEs, see Section 14.3.3 . | | | | | | | | | | | |

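### The medical-attention question is asked only for unsolicited AEs, so non-serious solicited reactions that lead to an unscheduled visit are not systematically ascertained for the 'all MAAEs' endpoint

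*Protocol*

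**What the plan says.** Protocol 3.2.2, repeated in SAP 3.2.2, sets the secondary safety endpoint as "Occurrence of all MAAEs, including NOCMCs and PIMMCs, from the time of the first study vaccination through approximately 12 months after the last study vaccination".

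Protocol 9.2.1 says how an event becomes an MAAE, and SAP 4.5.1 uses the same wording. It opens: "For each unsolicited AE experienced, the subject will be asked if he/she had received medical attention". Medical attention is "defined as hospitalization, an emergency room visit or an otherwise unscheduled visit to or from medical personnel for any reason". The rule then closes: "AEs characterized by such unscheduled medical care will be designated as MAAEs".

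Earlier in Protocol 9.2.1, the recording rule covers "AEs, including solicited injection site and systemic (subjective and quantitative) reactions, not meeting the protocol-defined criteria for SAEs", so solicited reactions are AEs. Protocol 9.2.2 also describes reactogenicity events as AEs.

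In the SAP shells, "Listing 13: 16.2.7.3 - Unsolicited Adverse Events" has a column containing "SAE? MAAE? PIMMC" flags. Listings 11 and 12, for solicited systemic and local events, have columns such as symptom and severity but nothing on medical attention or MAAE status.

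**The concern.** The endpoint speaks of all MAAEs, while the question that finds them covers only part of what the protocol calls AEs. The part left out is the 14 solicited terms (6 injection-site, 8 systemic) over Days 1 to 8 after each dose. These are the reactions most likely to be caused by the vaccine, in the period when they are most likely to occur.

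The displays affected are the MAAE row of Table 82, which is in the topline set, and the MAAE listing in Table 107. Protocol 11.6.2 expects few MAAEs, so a small number of omissions would be visible: one subject in an arm of 30 is 1/30 = 3.3 percentage points. If some sites flag such events and others do not, the count also becomes hard to interpret.

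**Working it through.** The plan states no figure on this point, so the check is mainly a comparison of text.

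**1. Scope of the rule against scope of the endpoint.** The endpoint covers all MAAEs. The question is asked for unsolicited AEs. The designating sentence says AEs, but its reference to such care points back to the care just asked about. No other section of either document asks the question for a solicited reaction.

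**2. The rule applied to four hypothetical records.**

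- Cough on Day 3, seen by a physician at an unscheduled visit: unsolicited, question asked, MAAE.
- Grade 3 fever on Day 2, seen in an emergency room and not admitted: solicited, question not asked, no stated route to an MAAE flag.
- Grade 3 injection-site pain on Day 3, with a prescription from an unscheduled visit: solicited, question not asked. Protocol 6.6 says a new medication should prompt evaluation for an MAAE, so this one may surface, but that section does not widen the definition. Protocol Table 6 makes the case realistic, because pain needing prescription medication is Grade 3.
- A solicited reaction with inpatient admission: meets an SAE criterion in Protocol 9.2.4 and is reported as an SAE. An emergency-room or urgent-care visit alone is not a listed SAE criterion.

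**3. The SAP shells.** Listing 13 has the flag; Listings 11 and 12 do not. Table 107 is organized by AE number and MedDRA term. The note to Table 83 states that it combines solicited, unsolicited and laboratory events. Tables 82 and 107 carry no such instruction for MAAEs.

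**4. Exposure.** Dose windows: 180 × 2 = 360. Windows after an AS03 dose: 180 primes + 4 arms × 30 boosts = 300, and 300/360 = 83%. The documents give no rate of medical attention for solicited reactions. For illustration only, assumed rates of 0.5%, 1% and 2% of doses give 360 × 0.005 = 1.8, 360 × 0.01 = 3.6 and 360 × 0.02 = 7.2 events at issue across the trial. These show scale under assumption and are not estimates.

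**The case against.** The strongest reply is that MAAE is a defined term and Protocol 9.2.1 is its definition. All MAAEs then means all events that meet it, and leaving reactogenicity to its own primary endpoint is a legitimate design choice. That is possible, but neither document says that the restriction is intended, and the unqualified designating sentence sits awkwardly with it.

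A reader might infer that solicited reactions are flatly barred from the MAAE count. The documents do not support that. No sentence excludes them, and a site could read the designating sentence together with the AE definition and flag a visit that a subject volunteers. SAP 9.4 describes Listing 13 as covering all reported AEs, although its title says unsolicited, and a missing column in a mock-up is not an exclusion rule. This softens the point without removing it: the question is still not asked, and counting could vary by site.

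It is also true that the events are not lost to the trial. Every solicited reaction counts toward a primary endpoint and is tabulated by severity and arm (Tables 84 to 94), with planned models that include boost dose. Interim history, medications and Memory Aids are reviewed about 1, 3 and 7 days after each dose, and subjects are told to report severe reactions. These contacts may bring some visits to light, but none requires the visit to be recorded as medical attention for a solicited reaction.

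A reader might further infer that the gap hides an adjuvant effect on MAAEs. Protocol 2.3.1 does report more solicited reactions with AS03 than with antigen alone. But all six arms receive an AS03 prime, so any difference could arise only after the boost. Assuming 2% per AS03 dose and 0.5% per unadjuvanted dose gives 30 × (0.02 + 0.02) = 1.2 events in each of Groups 1, 2, 4 and 5, against 30 × (0.02 + 0.005) = 0.75 in each of Groups 3 and 6. That gap of 0.45 events per arm rests entirely on rates with no source in the documents. MAAEs are to be reported by listing, with no planned test between arms.

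**Conclusion.** The point holds as a gap in ascertainment and an ambiguity in wording. A non-serious solicited reaction that leads to an emergency-room or other unscheduled visit is not systematically identified as an MAAE, and sites may treat such events differently. The SAE route and the new-medication prompt close the gap only in part.

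This rests on reading the designating sentence with the question before it, which is the natural reading rather than an express rule. The size of the undercount is unknown and may be small, and a claim of bias between arms is not supported. The affected endpoint is secondary, sparse and descriptive. The primary reactogenicity results are untouched. This is a low-cost improvement in safety ascertainment, not a threat to the trial's conclusions.

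**What to change.** In Protocol 9.2.1 and SAP 4.5.1 together, extend the question to every AE experienced, solicited or unsolicited. Record a yes/no medical-attention item for solicited events at the existing Memory Aid reviews. Carry the flag into Tables 82 and 107, and add the column to Listings 11 and 12. Keep these events out of the unsolicited-AE tables (97 to 105) so that they are not counted twice.

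A fallback is needed. Protocol 14.3 shows that this version was written after all subjects had enrolled, and enrollment and Dose 1 share Visit 01, so some dose reviews may already be closed. For those, obtain the item by data query. If that is not workable, label the endpoint and its tables 'unsolicited MAAEs' and state the exclusion.

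The cost is wording in two documents, one form item or a query, and two listing columns, with no extra visits or samples. The MAAE count may rise slightly, and the MAAE listing will no longer be a subset of the unsolicited-AE listing. Retrospective queries may also give less even ascertainment than asking at the time, which should be stated if they are used.
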